1. Has met criteria at any time during their life for a primary psychotic disorder (e.g. schizophrenia), or dementia.
2. Meets criteria for DSM-5-defined substance use disorder within three months of the screening visit.
3. Currently taking two or more antidepressants.
4. Presents with a clinically significant suicide risk, as assessed by a study physician.
5. Presence of any unstable or central nervous system-related medical illness that would interfere with cognition or participation.
6. Women who are currently pregnant or lactating, or plan to become pregnant during the study.

Setting

The setting of the study will occur in the Mood and Anxiety Disorders Program research clinic at the Emory University Executive Park campus.

Recruitment

Patients will be recruited through advertisements and clinician referral.

Procedures

The study consists of four visits.

Visit 1.

Visit 1 commences with the informed consent discussion and signing the informed consent form for the study. Subsequently, the following procedures will be performed:

1. Demographic information
2. Psychiatric interview and MINI.
3. Clinician ratings of symptoms: MADRS, HAMA
4. Clinician rating of suicidality: CSSRS
5. Clinician assessment of discontinuation symptoms present at baseline: DESS
6. Vital signs (temperature, height, weight, blood pressure, pulse)
7. Urine pregnancy test for women of child-bearing potential.
8. Medical History
9. Past psychiatric treatment history
10. Review of concomitant medications and supplements
11. Review of recall of side effects experienced when starting the antidepressant.
12. Patient questionnaires: DEBS, Q-LES-Q, BIS

Participants with internet access, either by cell phone or computer, will be asked to record their mood symptoms daily on the self-report Scale for Anxiety and Depression (SAD). This is a free internet app available at sad.ecu.edu.

Participants will use their de-identified study ID code as their login name to preserve confidentiality. After completing the scale in the office at Visit 1, participants will complete the SAD daily until Visit 4. Participants who lack internet access will be given paper versions of the form to fill out each day.

Upon completion of these components, the patient will be randomized to either Taper A or Taper B (see below). The physician will discuss the tapering process with the patient.

Visit 2

Visit 2 occurs 1 week after initiating the antidepressant taper. The following procedures will be performed:

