1. Clinician ratings of symptoms: MADRS, HAMA
2. Clinician rating of suicidality: CSSRS
3. Clinician assessment of discontinuation symptoms: DESS, PWC-20
4. Vital signs (temperature, height, weight, blood pressure, pulse)
5. Review of concomitant medications and supplements
6. Review of adverse events

7. Patient questionnaires: DEBS, BIS, PGI-C

Visit 3:

Visit 3 occurs 2 weeks after initiating the antidepressant taper. The following procedures will be performed:

1. Clinician ratings of symptoms: MADRS, HAMA
2. Clinician rating of suicidality: CSSRS
3. Clinician assessment of discontinuation symptoms: DESS, PWC-20
4. Vital signs (temperature, height, weight, blood pressure, pulse)
5. Review of concomitant medications and supplements
6. Review of adverse events
7. Patient questionnaires: DEBS, BIS, PGI-C

Visit 4:

Visit 4 occurs 3 weeks after initiating the antidepressant taper. The following procedures will be performed:

1. Clinician ratings of symptoms: MADRS, HAMA
2. Clinician rating of suicidality: CSSRS
3. Clinician assessment of discontinuation symptoms: DESS, PWC-20
4. Vital signs (temperature, height, weight, blood pressure, pulse)
5. Review of concomitant medications and supplements
6. Review of adverse events
7. Patient questionnaires: DEBS, BIS, PGI-C, Q-LES-Q
8. Planning of transition of care.
9. Download of SAD daily scale data from website sad.ecu.edu.

Multiple potential referral options will be discussed, depending on the patient's improvement and insurance status. Final referral selected will be based on the patient's preference. Options include referral to a primary care physician, psychiatrist, therapist, community mental health center, or other research studies. If necessary, patients may be seen for 1 or 2 post-study follow-up visits until their care transfer is completed.

Schedule of Events:

BIS: Barratt Impulsiveness Scale; CSSRS: Columbia Suicide Severity Rating Scale; DEBS: Dunlop Emotional Blunting Scale; DESS: Discontinuation Emergent Signs and Symptoms; HAM-A: Hamilton Anxiety Rating Scale; MADRS: Montgomery Asberg Depression Rating Scale; MINI: Mini-International Neuropsychiatric Interview; PGI-C: Patient Global Impression, Change; PWC-20: Physician Withdrawal Checklist; Q-LES-Q: Quality of Life Satisfaction Questionnaire

Visit Number	V1	V2	V3	V4
Day	0	7	14	21
Informed consent	X			
Demographics	X			
Vital signs	X	X	X	X
Weight	X			X
Psych/Medical History	X			
MINI v.7.0	X			
Clinician Ratings				
MADRS	X	X	X	X

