HAMA	X	X	X	X
DESS	X	X	X	X
PWC-20		X	X	X
Patient Ratings				
DEBS	X	X	X	X
BIS	X	X	X	X
Q-LES-Q	X			X
PGI-C		X	X	X
SAD (Daily)	X	X	X	X
Safety Measures				
Concomitant Meds	X	X	X	X
Adverse Events		X	X	X
CSSRS	X	X	X	X

Taper Regimens:

Taper A:

Days 1-7: Take 50% of baseline dose
Days 8-14: Take 25% of baseline dose
Day 15: Stop antidepressant

Taper B:

Days 1-3: Take 50% of baseline dose
Days 4-7: Take 25% of baseline dose
Day 8: Stop antidepressant

Monitoring for Suicidality

The emergence of suicidal thoughts or behaviors are not considered part of antidepressant discontinuation symptoms, but rather are thought to reflect the breakthrough of a new depressive episode. Patients who do not believe their antidepressant is helping them may nevertheless experience worsening depression with discontinuation of the medication. Therefore, we will conduct a standardized assessment for suicidal ideation or behavior, the CSSRS, at every study visit. Any patient who exhibits and increase in suicidal ideation, any form of suicidal behavior, or about whom the study physician has concern for their safety will be immediately withdrawn from the study and treated as clinically appropriate.

Operationalized Discontinuation Criteria for Suicidality:

Research participants are exited from the study should any of the following occur:

- Any emergent CSSRS defined suicidal behavior
- A suicidal ideation score of 5 (indicating active suicidal ideation with specific plan and some level of intent) on the CSSRS
- In the absence of a CSSRS suicidal ideation score of 5 or CSSRS-defined suicidal behavior, the investigator determines the patient to have a significant short-term risk for a suicide attempt.

Randomization:

Patients will be randomized in a 1:1 manner to Taper A or Taper B. Randomization will be stratified based on mechanism of action of drug (serotonin reuptake inhibitor or not). The two randomization schedules will be created prior to study commencement by a staff member not involved in the clinical components or data analytic components of the study. Randomization assignments will be placed in numbered and sealed envelopes, and opened sequentially for each subject who qualifies for randomization at Visit 1.

Included Medications:

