5. Scale for Anxiety and Depression (SAD). This 17-item scale is a self-report questionnaire asking about 17 common symptoms of depression over the past 24 hours and anxiety rated on a 1-10 visual analogue scale. The SAD is completed daily, providing a more fine-grained analysis of symptom change over short periods, such as tapering of antidepressants. The scale is accessed through a free internet app and takes approximately 3 minutes to complete.

Payment:

Patients will receive no compensation for participating in this study.

Outcomes:

Primary outcome:

The primary outcome is the change in the DESS, defined as the number of symptoms that are either new or worsened compared to baseline at Visit 4.

Secondary outcomes include:

1. Change in the PWC-20 from baseline to Visit 4
2. Number of patients who meet criteria for antidepressant discontinuation syndrome, defined as ≥ 4 new or worsened DESS symptoms, at visit during the study.

3. 3. Change in SAD daily score from baseline to peak SAD score during the taper period.

Statistical Analysis:

The primary analyses will be carried out on a modified intent to treat (ITT) sample, which will include all randomized patients who returned for at least one post-randomization study visit. The primary outcome variable is change in DESS score, defined as the number of symptoms that are either new or worsened at Visit 4 compared to baseline (Visit 1). For patients who terminate early the principle of last observation carried forward will be used. If amount of change for the total sample is non-normally distributed, raw change will be log-transformed to approximate a normal distribution before parametric tests are conducted. The primary analysis analyzing the taper groups will be an overall, 2-way ANCOVA, with appropriate covariates, on change in DESS score. Treatment groups will be compared on baseline variables that have a potential relationship to amount of change with the DESS. These include duration in months on ADM, dose equivalents of ADM at Visit 1, gender, age, Visit 1 HAMA score, Visit 1 MADRS score, and comorbid anxiety disorder. Only those Baseline variables that differ among randomized treatment groups at $P<0.10$ and are significantly associated with the primary outcome variable for the entire sample will be entered into the analysis as covariates.

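### Last observation carried forward fills the Visit 4 DESS with scores from different drug states in the two tapers, which can bias the primary comparison by an unknown amount and in either direction

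*Combined protocol and SAP*

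**What the plan says.** The Outcomes and Statistical Analysis sections define the primary outcome as the number of DESS symptoms new or worse at Visit 4 than at Visit 1. The analysis set is "all randomized patients who returned for at least one post-randomization study visit", so anyone analysed without a Visit 4 score has Visit 2, Visit 3 or both. The missing-data rule is one sentence: "For patients who terminate early the principle of last observation carried forward will be used". No other method, sensitivity analysis, expected dropout rate or visit window is given.

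The Procedures section and the Schedule of Events put Visits 2, 3 and 4 at Days 7, 14 and 21. Under Taper Regimens, Taper A takes half the baseline dose in the first week, then "Days 8-14: Take 25% of baseline dose", and stops on Day 15. Taper B is at a quarter of the baseline dose on Days 4 to 7, then "Day 8: Stop antidepressant".

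The Introduction defines the discontinuation syndrome by symptoms that arise after the drug is stopped. It adds that they mostly last under a week.

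**The concern.** Carrying a score forward assumes that the last value seen stands in for the value at Visit 4. Here the exposure under study changes between visits, and on a different calendar in each arm. At Visit 4 both arms are off drug. A score carried forward in Taper A comes from before the drug was stopped. A score carried forward in Taper B comes from before stopping if the last visit was Visit 2, and from after stopping if it was Visit 3. The rule therefore replaces unlike things in the two arms.

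If symptoms appear mainly after stopping, and patients leave in similar numbers at similar times, Taper A's mean is pulled down further than Taper B's. Part of an apparent benefit of the two-week taper could then come from the missing-data rule. The secondary PWC-20 and SAD analyses are to follow the same analytic plan, so the problem may extend to them.

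**Working it through.** **1. Drug state at each visit** (Procedures, Schedule of Events, Taper Regimens)

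| Visit | Day | Taper A | Taper B |
|---|---|---|---|
| 2 | 7 | 50% of baseline dose | 25% of baseline dose |
| 3 | 14 | 25% of baseline dose | off drug, 7 days after last dose |
| 4 | 21 | off drug, 7 days after last dose | off drug, 14 days after last dose |

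If the week is counted from Day 1 rather than Day 0, Visit 3 falls on Taper A's stop day and Visit 2 on Taper B's. These scores are still within about a day of the last dose.

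**2. The plan's own figure.** The Power Calculation section gives 80% power with 48 per group for a difference of 1.0 and SD 1.75, two-sided 5%. The standard error is 1.75 × √(2/48) = 0.357, and power is 79.9% (normal) or 79.1% (t). The figure reproduces and gives the yardstick: a target difference of 1.0 point.

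**3. Bias formula.** Assume equal true Visit 4 means. Let p2 and p3 be the proportions lost after Visits 2 and 3, and let H, Q and F be the mean counts at half dose, quarter dose and off drug.

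- Taper A mean is lowered by p2(F − H) + p3(F − Q).
- Taper B mean is lowered by p2(F − Q). Its Visit 3 leavers already carry an off-drug score.
- With equal loss, bias (B minus A) = p2(Q − H) + p3(F − Q). Positive values favour Taper A.

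**4. Numbers.** These inputs are assumptions, because the documents supply none of them: H = 0.5, Q = 1.0, F = 2.5 or 3.0, SD 1.75, 50 per arm, within-patient correlation 0.5. The type I error comes from simulation with 20,000 replicates; without dropout it is about 5%.

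| Lost after Visits 2 + 3, both arms | F | A lowered by | B lowered by | Bias | Type I error |
|---|---|---|---|---|---|
| 5% + 5% | 2.5 | 0.05×2.0 + 0.05×1.5 = 0.175 | 0.05×1.5 = 0.075 | 0.10 | about 6% |
| 5% + 5% | 3.0 | 0.05×2.5 + 0.05×2.0 = 0.225 | 0.05×2.0 = 0.10 | 0.125 | about 6% |
| 10% + 10% | 2.5 | 0.35 | 0.15 | 0.20 | about 8% |
| 10% + 10% | 3.0 | 0.45 | 0.20 | 0.25 | about 10% |

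**5. When the bias vanishes or reverses** (F = 2.5 unless stated)

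- Taper A loses 5% + 5% (lowered by 0.175). Taper B cancels this if it loses 0.175/1.5 = 11.7%, about 12%, after Visit 2.
- Leavers go in the week after stopping. Taper A then loses 10% after Visit 3 and Taper B loses 10% after Visit 2, all carrying a quarter-dose score. Both means fall by 0.10×1.5 = 0.15, so the bias is 0.
- 20% leave each arm, half of them after each visit. Taper A's on-drug scores are 1 point above its Visit 4 score, and Taper B's Visit 2 score is 1 point below its own. Taper A rises by 0.20×1 = 0.20 and Taper B falls by 0.10×1 = 0.10, so the bias is −0.30, favouring Taper B.

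**The case against.** The strongest reply is that the direction is not fixed by the documents. A reader might infer that early termination by itself produces a difference favouring Taper A, or that Taper B leavers will often carry an off-drug score. Neither is supported. Only Taper B patients who leave between Visits 3 and 4 carry an off-drug score, and nothing says how many there will be. If symptoms drive departure, the protocol's own premise suggests that Taper B leavers go soon after Day 8 and Taper A leavers soon after Day 15. Both then carry quarter-dose scores. If the faster taper also loses more patients, carry-forward favours Taper B.

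A reader might also infer that the same bias would hold whichever visit is primary. It would not. With Visit 3 primary and 10% lost after Visit 2, Taper A falls by 0.10×0.5 = 0.05 and Taper B by 0.15 to 0.20, which favours Taper B by 0.10 to 0.15.

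Nor does a net false positive for Taper A follow. At Visit 4 completers in Taper A are about one week off drug and those in Taper B about two. Since symptoms are said to be mostly short-lived, that imbalance leans toward Taper B and may partly offset the carry-forward effect. It is a separate matter, and two biases of unknown size do not correct each other.

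Finally, not every leaver's score is frozen before its peak. Taper B patients seen at Visit 3 are already a week past their last dose. DESS and CSSRS are collected at the same visits, so a patient withdrawn at a visit for suicidality may have that visit's DESS.

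These replies limit the claim about direction and size. They leave standing that the rule mixes drug states by arm and that no alternative or sensitivity analysis is planned.

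**Conclusion.** The concern holds in conditional form. For patients seen on schedule, the drug state behind a carried-forward score differs by arm; that follows from the protocol alone. The bias favours Taper A if off-drug scores exceed on-drug scores and loss is similar in amount and timing. Under the assumed means it is then modest at 10% total loss (0.10 to 0.13 points, 10 to 13% of the 1.0-point target). It becomes material at 20% (0.20 to 0.25 points). These sizes rest on assumed symptom means and dropout rates. Unequal loss, or symptoms peaking during the taper, can remove or reverse the bias. Confidence is moderate: firm on the mechanism, not on the net direction. The change is worth making because it is cheap and the bias cannot be bounded from the plan.

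**What to change.** In the Statistical Analysis section, replace carry-forward in the primary analysis with a likelihood-based repeated-measures model of the new-or-worsened DESS count at Visits 2, 3 and 4. Include arm, visit, arm-by-visit, drug-class stratum and baseline DESS, with unstructured covariance, and take the arm contrast at Visit 4. If the plan's non-normality rule is triggered, fit the model on the log scale or use a count model. Multiple imputation carried out separately by arm is an acceptable alternative.

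Keep carry-forward only as a sensitivity analysis. Add a second one in which patients who leave because of symptoms are imputed worse scores.

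The cost is SAP wording and slightly more analysis work; DESS is already scheduled at every visit. The new primary analysis relies on data being missing at random, which may fail if patients leave because of symptoms not yet recorded. The second sensitivity analysis is there to test that. The change does not address the unequal time off drug among completers at Visit 4, which needs its own resolution.

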Clinical practice would be enhanced if predictors of difficulty tapering ADM could be identified. Currently, very little is known about which patients are likely to develop discontinuation symptoms. The most consistently replicated finding is that the long half-life antidepressant fluoxetine is associated with fewer discontinuation symptoms than the short half-life agent paroxetine. However, discontinuation symptoms are known to arise with fluoxetine cessation, and both these drugs are SSRIs. Identification of patients who will or will not develop difficulty coming off antidepressants is of significant clinical importance because tapers that are longer or shorter than necessary can negatively impact patient care.

This study will aim to assess the frequency of discontinuation symptoms across all classes of antidepressants among patients who have not responded to medication. Only patients who wish to be tapered off their medication will be eligible to participate.

Objectives:

There are two primary objectives to this study:

AIM 1: Compare the tolerability of two antidepressant tapering regimens.

Hypothesis 1. Tapering antidepressant dose over two weeks will be associated a lower incidence of antidepressant discontinuation symptoms than tapering over one week.

Hypothesis 2. Discontinuing medications that inhibit the serotonin transporter (SSRIs and SNRIs) will show greater difference in the frequency of discontinuation symptoms between the two week and one-week tapering regimens than medications that do not inhibit the serotonin transporter.

AIM 2: Identify demographic and clinical features that predict the emergence of antidepressant discontinuation symptoms.

Hypothesis 2. SSRIs and SNRIs will be associated with greater numbers of discontinuation symptoms compared to non-SSRI/SNRI medications.

Hypothesis 1. Duration of treatment will positively associated with the number of discontinuation symptoms.

Study Design and Methods:

Sample

The sample will include 125 subjects currently taking an FDA-approved antidepressant. We anticipate an approximate screen fail rate of 20%, allowing for 100 subjects to enter randomization.

Inclusion Criteria:

1. Male or female, age 18-75
2. Currently taking an FDA-approved antidepressant for at least four weeks.
3. Primary psychiatric diagnosis of major depressive disorder, an anxiety disorder, OCD, or PTSD.
4. Ability to read and understand English language

Exclusion Criteria for all Subjects:

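### The primary ANCOVA adjusts for a prognostic baseline variable only if it is imbalanced by chance, and its conditional log step has no trigger and is undefined for a patient with no symptoms

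*Combined protocol and SAP*

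**What the plan says.** All of this is in the Statistical Analysis section unless noted.

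- **Outcome.** Change in DESS, "defined as the number of symptoms that are either new or worsened at Visit 4 compared to baseline (Visit 1"). It is a count with minimum 0.
- **Sample.** Modified intent-to-treat: "all randomized patients who returned for at least one post-randomization study visit".
- **Model.** "an overall, 2-way ANCOVA, with appropriate covariates, on change in DESS score". The second factor is not named. Randomization is stratified by drug mechanism (serotonin reuptake inhibitor or not).
- **Covariates.** Seven candidates are named: duration on medication, dose equivalents, gender, age, Visit 1 HAMA, Visit 1 MADRS and comorbid anxiety disorder. The entry rule is "Only those Baseline variables that differ among randomized treatment groups at $P<0.10" and that "are significantly associated with the primary outcome variable for the entire sample will be entered into the analysis as covariates". No significance level is given for the association.
- **Transformation.** "If amount of change for the total sample is non-normally distributed, raw change will be log-transformed to approximate a normal distribution". No normality criterion, added constant or rule for zeros is given here or elsewhere.
- **Secondary analyses.** PWC-20 and SAD peak score follow the same plan.
- **Power Calculation.** 48 per group, 80% power, a difference of 1.0 DESS points, SD 1.75, two-sided 0.05: the raw scale.
- **Objectives, Aim 2.** "Duration of treatment will positively associated with the number of discontinuation symptoms".

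**The concern.** In a randomised trial a baseline difference between arms is a chance event. Adjustment earns its precision from a covariate's relation to the outcome, whether or not the covariate is imbalanced. Requiring imbalance first discards most of the available gain, and the second screen makes the final model depend on the outcome data. The plan thus expects duration to predict symptom number, yet adjusts for it only by accident.

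The log step is a separate gap. Taken literally, it asks for the log of 0 for every patient with no new or worsened symptom. Whether the step is used at all depends on an unnamed criterion, and once it is used the comparison is no longer of the mean counts on which the trial was powered.

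**Working it through.** **1. The plan's sample size.** n per arm = 2 × (1.960 + 0.842)² × 1.75² / 1.0² = 48.07. At 48 per arm power is 79.9% (normal) or 79.1% (t-test). The stated figure reproduces, with no margin to spare.

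**2. How often the screen admits a variable.** The balance test passes a given variable in about 10% of trials, however prognostic it is. With seven independent candidates, at least one passes in 1 − 0.9⁷ = 52% of trials. The association test lowers entry further.

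**3. What that costs.** The documents give no R-squared, so 0.1, 0.2 and 0.3 are assumed. Simulation, 10,000 trials per setting: 48 per arm; negative binomial counts, means 1.5 and 2.5, SD 1.75; seven candidates, of which duration, HAMA and MADRS are prognostic; association tested at 0.05 (assumed); arm and stratum always in the model.

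| R-squared | 0.1 | 0.2 | 0.3 |
|---|---|---|---|
| A given prognostic covariate enters | 4% | 7% | 9% |
| No covariate enters | 85% | 79% | 74% |
| Power, plan's rule | 78% | 78% | 79% |
| Power, all seven fixed (HC2) | 79% | 83% | 87% |
| Type I error, plan's rule | 4.7% | 4.4% | 3.8% |

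A repeat gave 78 / 79 / 81% under the rule and 81 / 84 / 89% with all seven fixed. With a normal outcome and one prognostic covariate, the formula with SD × √(1 − R-squared) gives 83.9 / 87.9 / 91.7% for fixed adjustment, and simulation gives 82.8 / 87.0 / 90.5%, against 79.0 / 80.0 / 80.2% under the rule. At R-squared 0.1 the gain is small.

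**4. Zeros.** The means are assumed, and the SD is the plan's.
- SD 1.75 in each arm: the zero probabilities are 0.358 (mean 1.5) and 0.105 (mean 2.5), so 48 × (0.358 + 0.105) = 22 of 96 patients.
- Common dispersion k = 4, which gives an average variance of 2 + 4.25/4 = 3.0625 = 1.75²: the probabilities are 0.280 and 0.143, so 48 × 0.423 = 20 of 96.

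**5. The trigger decides.** In these two settings (equal SD / common dispersion) the log is triggered in 2 / 4% of trials by |skewness| > 2, in 51 / 68% by skewness > 1 and in 100 / 100% by Shapiro-Wilk at 0.05. The raw count and log(x+1) reach different verdicts at 0.05 in 13 / 9% of trials. The choice between +1 and +0.5 matters little (2 / 3%).

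**6. Type I error.** With one distribution in both arms, a trigger fixed in advance on pooled data followed by log(x+1) gives 4.3-5.1%. At means of 2.0, reporting whichever of raw, +1 and +0.5 is significant gives 7.2%, or 8.8% if +0.01 is also tried.

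**7. The log tests something else.** With equal means of 2.0 but variances of 3.9 and 2.2 (assumed for illustration; the plan gives one SD), the raw analysis rejects in 5.6% of trials and log(x+1) in 9.5%.

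**The case against.** The strongest defence has four parts.

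- **The plan's rules are blind to arm where it matters most.** Both the normality decision and the association test use the whole sample. A stated pooled trigger with log(x+1) would hold about 5% when the arms share one distribution. This stands: the fault is that the trigger and constant are not stated.
- **The covariate gain rests on an R-squared that the documents do not give.** This also stands. At 0.1 the gain is 1 to 3 points, and if no covariate is prognostic, fixing them loses a little power. But the screen has no compensating benefit, since it is already conservative.
- **Dropping the log can cost power.** In the equal-SD setting raw counts give about 78-79% against 91-92% for log(x+1). At means 1 and 2 the figures are 78% and 95%. Under common dispersion the order reverses (80% against 76%). This is a real trade-off, and it turns on how the variance differs between arms. The equal-SD setting is somewhat artificial, because it needs very different dispersion in the two arms (k = 1.44 and 11.1). The argument for the raw scale is that it keeps the difference for which the trial was sized.
- **The choice of covariates is partly preference.** Agreed. The plan already says that all seven may relate to the outcome, so they are the natural default.

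**Conclusion.** The point holds as one of precision and specification, and the plan should be changed. The screen leaves out a prognostic covariate about 90% of the time or more. For assumed R-squared of 0.1 to 0.3, that means power of about 78-81% instead of about 81-89%. The log step cannot be run as written on the modified intent-to-treat sample. That conclusion needs only one patient with a count of 0; the figure of about 20 of 96 rests on the assumed means and negative binomial shape.

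A reader might infer more than the documents support:

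- **That the plan inflates type I error.** The covariate rule is conservative, and a pooled log rule fixed in advance holds about 5% when the arms share one distribution. The 7-9% figures arise only if the version is chosen after the results are seen, which the plan does not propose.
- **That patients without symptoms would be dropped.** The sample definition does not allow it.
- **That the stratum and Visit 1 DESS are excluded.** They are only unnamed. The list of candidates is open-ended. Drug class is probably the second factor of the 2-way model, since Aim 1 states that "Discontinuing medications that inhibit the serotonin transporter (SSRIs and SNRIs) will show greater difference in the frequency of discontinuation symptoms" between the regimens.
- **That the sample size is wrong.** It reproduces.

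**What to change.** 1. Delete the imbalance and association screen. Always include taper arm, the drug-class randomisation stratum (stated to be the second factor of the 2-way ANCOVA) and a covariate list fixed in advance. By default this is the seven variables already named, with Visit 1 DESS as an optional addition.
2. Delete the conditional log step. Analyse the untransformed number of new or worsened symptoms at Visit 4, and report the adjusted mean difference with robust (HC2) standard errors. Add a negative binomial model as a sensitivity analysis.
3. Make the same change in both secondary analyses that follow this plan, PWC-20 and SAD peak score. A SAD change can be zero or negative, so the log fails there too.

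**Cost.** Only wording changes: every term is the stratification factor or is already collected at Visit 1, and 48 per group stands. The downside is about 1-3 points of power if the covariates are not prognostic. Against log(x+1), the raw-scale test may have clearly less power (about 79% against 92% at means 1.5 and 2.5 with equal SD) or slightly more (80% against 76% under common dispersion). That is accepted to keep the 1.0-point difference as the quantity tested.
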